Teclistamab, another BCMA BsAb, was approved in October 2022, based on results from the MajesTEC-1 trials; the ORR was 63.0%, and common adverse events included infections (76.4%), cytokine release syndrome (72.1%), anemia (52.1%), and neutropenia (70.9%). Elranatamab was approved in August of 2023, based on the results from the MagnetisMM-3 trial, a phase 2 trial aimed at assessing the efficacy of elranatamab monotherapy. The ORR was 61.0%, and common adverse events included infections (69.9%), cytokine release syndrome (57.7%), anemia (48.8%), and neutropenia (48.8%). While some published studies have assessed the real-world utilization of other BCMA BsABs such as teclistamab, the real-world usage of elranatamab has not been characterized. This study aims to describe the uptake and use of elranatamab subsequent to the August 2023 Food and Drug Administration (FDA) approval.

This noninterventional study is designated as a PASS and is conducted voluntarily by Pfizer.

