		of administration is intravenous for an intravenous anti-infective (dichotomous)	
1	Neutropenia	Medical claim with an ICD-10 code in the inpatient or non-IP setting for neutropenia (dichotomous)	MM diagnosis to 1 day prior to index date
1	Hypercalcemia	Medical claim with an ICD-10 code in the inpatient or non-IP setting for hypercalcemia (dichotomous)	MM diagnosis to 1 day prior to index date
1	Hepatotoxicity	Medical claim with an ICD-10 code in the inpatient or non-IP setting for hepatotoxicity (dichotomous)	MM diagnosis to 1 day prior to index date
1	Renal failure	Medical claim with an ICD-10 code in the inpatient or non-IP setting for renal failure (dichotomous)	MM diagnosis to 1 day prior to index date
1	Amyloidosis	Medical claim with an ICD-10 code in the inpatient or non-IP setting for amyloidosis (dichotomous)	MM diagnosis to 1 day prior to index date
1	Hypertension	Medical claim with an ICD-10 code in the inpatient or non-IP setting for hypertension (dichotomous)	MM diagnosis to 1 day prior to index date
1	Extramedullary disease	Medical claim with an ICD-10 code in the inpatient or non-IP setting for extramedullary disease (dichotomous)	MM diagnosis to 1 day prior to index date
1	Charlson Comorbidity Index (CCI) score	CCI ¹⁸ (continuous and categorical): • 0 (no comorbidities) • 1 to 2 (mild) • 3 to 4 (moderate) • ≥ 5 (severe)	180 days prior to index date to index
1	Myocardial infarction	Medical claim with an ICD-10 code in the inpatient or non-IP setting for myocardial infarction (dichotomous)	180 days prior to index date to index
1	Congestive heart failure	Medical claim with an ICD-10 code in the inpatient or non-IP setting for congestive heart failure (dichotomous)	180 days prior to index date to index date

Objective	Variable	Definition	Assessment Period(s)
1	Peripheral vascular disease	Medical claim with an ICD-10 code in the inpatient or non-IP setting for peripheral vascular disease (dichotomous)	180 days prior to index date to index
1	Cerebrovascular disease	Medical claim with an ICD-10 code in the inpatient or non-IP setting for cerebrovascular disease (dichotomous)	180 days prior to index date to index
1	Dementia	Medical claim with an ICD-10 code in the inpatient or non-IP setting for dementia (dichotomous)	180 days prior to index date to index
1	Chronic pulmonary disease	Medical claim with an ICD-10 code in the inpatient or non-IP setting for chronic pulmonary disease (dichotomous)	180 days prior to index date to index

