1	Rheumatic disease	Medical claim with an ICD-10 code in the inpatient or non-IP setting for rheumatic disease (dichotomous)	180 days prior to index date to index
1	Peptic ulcer disease	Medical claim with an ICD-10 code in the inpatient or non-IP setting for peptic ulcer disease (dichotomous)	180 days prior to index date to index
1	Liver disease	Medical claim with an ICD-10 code in the inpatient or non-IP setting for liver disease (dichotomous)	180 days prior to index date to index
1	Diabetes	Medical claim with an ICD-10 code in the inpatient or non-IP setting for diabetes (dichotomous)	180 days prior to index date to index
1	Renal disease	Medical claim with an ICD-10 code in the inpatient or non-IP setting for renal disease (dichotomous)	180 days prior to index date to index date
1	Hemiplegia or paraplegia	Medical claim with an ICD-10 code in the inpatient or non-IP setting for hemiplegia or paraplegia (dichotomous)	180 days prior to index date
1	Human immunodeficienc y virus	Medical claim with an ICD-10 code in the inpatient or non-IP setting for human immunodeficiency virus (dichotomous)	180 days prior to index date to index date

Objective	Variable	Definition	Assessment Period(s)
1	Metastatic solid tumor	Medical claim with an ICD-10 code in the inpatient or non-IP setting for metastatic solid tumor (dichotomous)	180 days prior to index date to index date

Table 3 includes definitions and assessment periods for all study variables being used as outcomes. The full code list can be found in ANNEX 2. ADDITIONAL INFORMATION. If applicable, the frequency and percentage of patients with missing data for each variable will be described.

Table 3. Key Variables of Interest

Objective	Variable	Definition	Assessment Period(s)
Treatment ex	posure		
2	Use of supportive MM medications	Medical or pharmacy claim with evidence of an NDC, HCPCS, generic name or CPT code for the following medications (dichotomous):	Index date to the end of follow-up Index date Step-Up Dosing Period Maintenance Periods
2	Reported vial size	Reported vial size in the following categories (categorical): • Unknown vial – inpatient dose • 44mg/1.1mL • 76mg/1.9mL • Missing dose/unknown dose For the cohort of teclistamab patients the reported vial size (categorical): • Unknown vial – inpatient dose • 30mg/3mL • 153mg/7mL • Missing dose/unknown dose	Index date to the end of follow-up Index date Step-Up Dosing Period Maintenance Periods

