Exploratory Obj 1	Cytokine release syndrome (CRS) ¹	Medical claim with an ICD-10 code in the inpatient, non-IP or pharmacy setting for CRS, categorized into the following grades (categorical): • Any (all grades and unspecified grade) • Grade 1 • Grade 2 • Grade 3 • Grade 4 • Grade 5 If patients have multiple, conflicting grades, then the highest recorded grade will be reported	Index date to end of follow-up, where follow-up will be based on last dose of elranatamab or teclistamab (e.g., 14 days after last recorded dose or 90 days after last recorded dose).
Exploratory Obj 1	Cytokine release syndrome (CRS) ¹ symptoms	Medical claim with an ICD-10 code in the inpatient, non-IP or pharmacy setting for CRS symptoms, per a algorithmic type approach (e.g., Keating algorithm, identifying patients with fever, hypotension, fatigue, headaches, hypoxia)	Index date to end of follow-up, where follow-up will be based on last dose of elranatamab or teclistamab (e.g., 14 days after last recorded dose or 90 days after last recorded dose).
Exploratory Obj 1	Immune effector cell-associated neurotoxicity syndrome (ICANS)	Medical claim with evidence of an ICD-10 code in the inpatient, non-IP or pharmacy setting for ICANS, categorized into the following grades (categorical): • Any (all grades and unspecified grade) • Grade 1 • Grade 2 • Grade 3 • Grade 4 • Grade 5 If patients have multiple, conflicting grades then the highest recorded grade will be reported	Index date to end of follow-up, where follow-up will be based on last dose of elranatamab or teclistamab (e.g., 14 days after last recorded dose or 90 days after last recorded dose).
Hematologic	events		
Exploratory Obj 1	Anemia ¹	Medical claim with an ICD-10 code in the inpatient, non-IP, or pharmacy setting for anemia (dichotomous)	Index date to end of follow-up, where follow- up will be based on last dose of elranatamab or teclistamab (e.g., 14 days after last recorded dose or

			90 days after last recorded dose).
Exploratory Obj 1	Lymphopenia ¹	Medical claim with an ICD-10 code in the inpatient, non-IP, or pharmacy setting for lymphopenia (dichotomous)	Index date to end of follow-up, where follow-up will be based on last dose of elranatamab or teclistamab (e.g., 14 days after last recorded dose or 90 days after last recorded dose).
Non-hematol	ogic events		

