	Clinical, Adverse event		E13.41, G57.70, G57.71, G57.72, G57.73, G59, G57.80, G57.81, G57.82, G57.83, G58.8, G58.9, G64., G61.0, M05.50, M05.511, M05.512, M05.519, M05.521, M05.522, M05.529, M05.531, M05.532, M05.539, M05.541, M05.542, M05.549, M05.551, M05.552, M05.559, M05.551, M05.552, M05.559, M05.571, M05.572, M05.579, M05.59, E08.40, E08.42, E09.40, E09.42, E10.40, E10.42, E11.40, E11.42, E13.40, E13.42, G13.0, G13.1, A36.83, A52.15, G63, M34.83, G62.1, G61.1, G62.0, G62.2, G62.82, G61.81, G62.81, G61.89, G62.89, G61.9, G62.9, H46.3, M54.10, M54.18, M79.2, R20.0, R20.1, R20.2, R20.3, R20.8, R20.9
Any infection	Baseline characteristic - Clinical	Claims data	An ICD-10 Diagnosis Code for any of the following types of infections. See the rows below for codes for each infection type. COVID-19, Adenoviral pneumonia, Cytomegaloviral pneumonitis, Other Pneumonia, Upper respiratory tract infection, Sepsis, Cytomegaloviral infection, Pneumocystis jiroveci pneumonia (PJP), Hepatitis C, Hepatitis B, Other infectious hepatitis, Helicobacter pylori, Candida esophagitis, Urinary tract infection
Use of intravenous anti- infective	Baseline characteristic - Clinical	Claims data	See "Antivirals" and "Antibiotics" above
Neutropenia	Baseline characteristic - Clinical, Adverse event	Claims data	ICD-10 Diagnosis: D70x
Hypercalcemia	Baseline characteristic - Clinical	Claims data	ICD-10 Diagnosis: E83.52
Hypoxia	Baseline characteristic - Clinical, Adverse event	Claims data	ICD-10 Diagnosis: J96.20, J96.11, J96.90, J96.01, J96.00, J96.10, J96.21, J96.91, I27.23, R09.02
Hepatotoxicity	Baseline characteristic - Clinical, Adverse event	Claims data	ICD-10 Diagnosis: K71.x
Renal failure	Baseline characteristic -	Claims data	ICD-10 Diagnosis: N17x, N18x, N19x, R34x, T82.4, Z49.02, Z99.2

	Clinical, Adverse event		
Amyloidosis	Baseline characteristic - Clinical	Claims data	ICD-10 Diagnosis: E85.4x, E85.8x, E85.9x
Hypertension	Baseline characteristic - Clinical	Claims data	ICD-10 Diagnosis: I10x-I15x, I16x
Extramedullary disease	Baseline characteristic - Clinical	Claims data	ICD-10 Diagnosis: C90.2x
CCI score	Baseline characteristic - Clinical	Claims data	See components below
Myocardial infarction	Baseline characteristic - Clinical	Claims data	ICD-10 Diagnosis: I21.x, I22.x, I25.2
Congestive heart failure	Baseline characteristic - Clinical	Claims data	ICD-10 Diagnosis: I11.0, I13.0, I13.2, I25.5, I42.0, I42.5, I42.6, I42.7, I42.8, I42.9, I43.x, I50.x, P29.0

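### Annex 2 lists neutropenia as an adverse event, but Table 3 has no neutropenia row, so it would not be reported after index

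*Protocol*

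**What the plan says.** Four places in the protocol bear on this.

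- **Section 7 (rationale).** For elranatamab it reports that "common adverse events included infections (69.9%), cytokine release syndrome (57.7%), anemia (48.8%), and neutropenia (48.8"%), and for teclistamab that "common adverse events included infections (76.4%), cytokine release syndrome (72.1%), anemia (52.1%), and neutropenia (70.9"%).
- **Section 9.3, Table 2.** Neutropenia is a baseline variable under Objective 1: "Medical claim with an ICD-10 code in the inpatient or non-IP setting for neutropenia (dichotomous"). Its window runs from MM diagnosis to the day before index.
- **Section 9.3, Table 3.** The introduction says "Table 3 includes definitions and assessment periods for all study variables being used as outcomes". The hematologic block has two rows, anemia and lymphopenia. The second is defined as "Medical claim with an ICD-10 code in the inpatient, non-IP, or pharmacy setting for lymphopenia (dichotomous"), and the non-hematologic block follows directly.
- **Annex 2.** The neutropenia row has the role "Baseline characteristic - Clinical, Adverse event" and the code "ICD-10 Diagnosis: D70x".

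Section 9.7.6 estimates prevalence and incidence for the adverse events in Table 3, with a washout that depends on the event and is also taken from Table 3. Section 9.8 says the protocol is to be followed strictly.

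**The concern.** The protocol holds two different lists of adverse events. Annex 2 counts neutropenia as one; Table 3, which drives the analysis, does not. An analyst working from Table 3 leaves neutropenia out of the safety tables. An analyst working from Annex 2 includes it but has no assessment window and no washout with which to define an incident case.

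At stake is the completeness of Exploratory Objective 1 (tolerability and real-world safety) and of its repetition in the teclistamab cohort under Exploratory Objective 3. The safety report would give a baseline frequency of neutropenia with no on-treatment figure beside it, although the protocol's own background presents neutropenia as a common event of both drugs.

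**Working it through.** The plan states no figure to reproduce; the check is a comparison of lists.

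**Step 1. The four adverse events named in section 7 against Table 3.**

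| Event | Elranatamab trial | Teclistamab trial | Outcome in Table 3 |
|---|---|---|---|
| Infections | 69.9% | 76.4% | Yes, a block of individual infections |
| CRS | 57.7% | 72.1% | Yes |
| Anemia | 48.8% | 52.1% | Yes, 30-day washout |
| Neutropenia | 48.8% | 70.9% | No |

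Three of the four have rows. The missing one is cited at the same rate as anemia for elranatamab. For teclistamab it is cited 70.9 − 52.1 = 18.8 percentage points above anemia.

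**Step 2. Annex 2 rows with the dual role (baseline and adverse event) against Table 3.**

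| Annex 2 row | Own row in Table 3 |
|---|---|
| Peripheral neuropathy | Yes |
| Hepatotoxicity | Yes |
| Renal failure | Yes |
| Hypoxia | No; named only as an example of a CRS symptom |
| Neutropenia | No; not mentioned anywhere in Table 3 |

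Conditions meant only for baseline, such as hypercalcemia, amyloidosis and hypertension, carry the baseline role alone. The dual role therefore normally marks a post-index outcome, and neutropenia is the one dual-role variable absent from Table 3 altogether.

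**Step 3. Whether another rule brings neutropenia back.** The Table 3 footnotes set washouts of 30, 60 and 14 days, each attached to named rows; none is attached to neutropenia. The only tabulated definition is the Table 2 variable, whose window closes the day before index. Section 9.7.6 takes its events from Table 3. No other section of the protocol analyses post-index neutropenia.

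**Step 4. Whether the document explains the omission.** Section 9.9 notes that hematological toxicities are often defined by laboratory cutoffs that claims lack, and says that ICD codes are used instead. Anemia and lymphopenia are kept on that basis, so it gives no reason for dropping neutropenia alone. The abstract's short list of adverse events omits neutropenia, but it omits anemia and lymphopenia as well, so it does not settle the matter.

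**The case against.** **The Annex 2 label may be a leftover.** The role column does not track the variable tables perfectly. Hypoxia has the dual role without its own outcome row, and acute graft versus host disease is labelled a baseline characteristic without a Table 2 row. This stands in part: the label alone does not prove that a neutropenia outcome was intended, so removing the label is a legitimate way to resolve the conflict. It does not remove the contradiction, and the rationale points towards including the event.

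**The row may have been lost when the PDF was read.** Parts of Table 3 are visibly damaged, notably the cost rows. The hematologic block, however, reads without a break from its header through anemia and lymphopenia to the next header. Loss there is unlikely, though the extracted text cannot exclude it.

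**The SAP may deal with it.** Section 9.7 lets the SAP modify the protocol's plans. But this document itself states both lists, so the conflict exists whatever the SAP adds.

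**The weight is limited.** Safety is an exploratory objective in a descriptive study without formal comparisons. That stands, and no primary objective is touched.

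**A stronger reading to avoid.** A reader might multiply the trial rate by the count in section 9.5, 0.488 × 133 ≈ 65, and conclude that about 65 elranatamab patients would have an untabulated event. The document does not support this. The 133 are patients with an elranatamab claim as of August 2024, with no stated application of the eligibility criteria, and data now run to December 2025. Section 9.9 also says that milder events may not be captured in claims, so a trial rate need not carry over to D70x codes. A reader might likewise argue that the gap matters because neutropenia raises infection risk; the protocol makes no such statement.

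**Conclusion.** The inconsistency is confirmed. Annex 2 assigns neutropenia an adverse-event role, section 7 names it as common for both drugs, and the one table that governs the safety analysis leaves it out. Under the plan as written, post-index neutropenia would be reported in neither cohort.

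The size can be stated only as one of four named adverse events per drug. The number of patients cannot be derived, because the document gives neither a claims-based rate nor a post-eligibility cohort size. The conclusion assumes that the hematologic block of Table 3 is complete as read, and that the analysis follows Table 3 as sections 9.7.6 and 9.8 require. It is worth correcting before the final analysis planned for February 2026, with weight limited by the exploratory status of the objective.

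**What to change.** Reconcile Annex 2 with Table 3.

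- **Preferred.** Add a neutropenia row to the hematologic block of Table 3, using the existing D70x code and the windows already set for the other events (index to 14 days and to 90 days after the last dose). State its washout. The 30 days used for anemia and lymphopenia is the natural analogue, but the document sets none for neutropenia, so the study team must choose and record one.
- **Alternative.** Remove the adverse-event role from the Annex 2 row and state why an event named in the rationale is not reported after index.

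The preferred change costs one table row with its washout footnote and the matching output for each cohort. No new code list is needed, because the neutropenia code is already in Annex 2.

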2	Average time between elranatamab or teclistamab claims	Sum of the days between claims for the index drug (continuous) divided by the total number of administrations -1	Index date to the end of follow-up Step-Up Dosing Period

	1	T	T
			Maintenance Periods
2	Frequency of elranatamab or	Total number of inpatient, non-IP, and pharmacy claims of the index drug during the	Index date to the end of follow-up
	teclistamab claims	time period based on vial size (continuous)	Step-Up Dosing Period
			Maintenance Periods
2	Relative Administration Intensity (RAI)	The ratio of the actual administrations received divided by the expected number of administrations according to the US label	Index date to the end of follow-up
		(continuous)	Step-Up Dosing Period
			Maintenance Periods
2	Time to Discontinuation (TTD)	Time in months from first administration until last administration prior to treatment discontinuation (continuous). Treatment discontinuation is defined as an 8-week gap in elranatamab or teclistamab therapy, next treatment after index treatment (CAR-T, BsABs, bendamustine or belantamab), or death.	Index date to the end of follow-up
2	Reason for Discontinuation	Reason for treatment discontinuation used to estimate time to discontinuation, either an 8-week gap in elranatamab or teclistamab therapy, next treatment after index treatment (CAR-T, BsABs, bendamustine or belantamab), or death.	Index date to the end of follow-up
Health care	resource utilization an	d costs	
3	All-cause IP visits	Medical claim for IP (non-emergency department [ED]) visit (dichotomous)	Start of data to 1 day before index date, index date until last recorded dose, and time from discontinuation through time of censoring
		Number of IP (non-ED) visits (continuous)	
3	All-cause OP visits	Medical claim for non-IP/non-ED visit (dichotomous)	Start of data to 1 day before index date, index date until last recorded dose, and time from
		Number of non-IP/non-ED visits (continuous)	discontinuation through time of censoring

3	All-cause ED visits	Medical claim for ED visit (dichotomous) Number of ED visits (continuous)	Start of data to 1 day before index date, index date until last recorded dose, and time from discontinuation through time of censoring
3	All-cause pharmacy claims	Pharmacy claim (dichotomous) Number of pharmacy claims (continuous)	Start of data to 1 day before index date, index date until last recorded dose, and time from discontinuation through time of censoring

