9.7.3. Healthcare Resource Utilization and Cost

All-cause HCRU and MM-related HCRU (i.e., HCRU with a diagnosis code or treatment for MM) will be measured as the total number of per-patient-per-month (PPPM) IP, OP, ED, and pharmacy claims that occurred over the follow-up period. Medical claims will only be counted once per day to estimate visits. Additionally, the total length of IP stays will be reported among patients with at least one IP visit. Given the recency of the study period, costs will not be adjusted for inflation.

HCRU and costs will be measured across three different time periods: from the start of data to a day before the index date, from the index date until last recorded dose, and the time from discontinuation through the time of censoring. Patients will be censored at the earliest of death, next treatment (CART, BsABs, bendamustine or belantamab), the end of part A or B continuous closed-claim coverage, or the end of data.

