Use of premedication	Outcome - Dosing and Administration Patterns	Claims data	HCPCS: J1094, J1096, J8540, J1100, J0131, J7637, J7638, J7312, J1200, Q0163 Generic names (and associated NDCs): Acetaminophen, Dexamethasone, Diphenhydramine
Inpatient	Baseline characteristic, Outcome - HCRU	Claims data	Any event in the inpatient table or an event in the non-inpatient table where acute_subacute is "acute inpatient" or where utilization type is "professional services", and service subcategory contains the term "hospital/IP encounter"
Outpatient	Baseline characteristic, Outcome - HCRU	Claims data	Any event in the non-inpatient table where utilization type is outpatient and service subcategory is not "emergency dept encounter"

Emergency department	Baseline characteristic, Outcome - HCRU	Claims data	Any event in the non-inpatient table where utilization type is "outpatient" and service subcategory is "emergency dept encounter"
Cytokine release syndrome (CRS)	Safety events	Claims data	ICD-10 Diagnosis: D89.83x
Immune effector cell- associated neurotoxicity Syndrome (ICANS)	Adverse events	Claims data	ICD-10 Diagnosis: G92.0x
Anemia	Adverse events	Claims data	ICD-10 Diagnosis: D46.0, D46.1, D46.20, D46.21, D46.22, D46.4, D46.9, D46.A, D46.B, D46.C, D46.Z, D47.4, D50.0, D50.1, D50.8, D50.9, D51.0, D51.1, D51.2, D51.3, D51.8, D51.9, D52.0, D52.1, D52.8, D52.9, D53.0, D53.1, D53.2, D53.8, D53.9, D55.0, D55.1, D55.2, D55.21, D55.29, D55.3, D55.8, D55.9, D59.0, D59.1, D59.10, D59.11, D59.12, D59.13, D59.19, D59.2, D59.3, D59.30, D59.31, D59.39, D59.4, D59.5, D59.6, D59.8, D59.9, D60.0, D60.1, D60.8, D60.9, D61.01, D61.09, D61.1, D61.2, D61.3, D61.810, D61.811, D61.818, D61.82, D61.89, D61.9, D63.0, D63.1, D63.8, D64.9, D75.81
Lymphopenia	Adverse events	Claims data	ICD-10 Diagnosis: D72.810
Hypogammaglobulinemia	Adverse events	Claims data	ICD-10 Diagnosis: D80.1, D80.3, D80.9
Hypophosphataemia	Adverse events	Claims data	ICD-10 Diagnosis: E83.39
Hypokalaemia	Adverse events	Claims data	ICD-10 Diagnosis: E87.6
Arthralgia	Adverse events	Claims data	ICD-10 Diagnosis: M25.5x
Pyrexia	Adverse events	Claims data	ICD-10 Diagnosis: R50.x
Hypotension	Adverse events	Claims data	ICD-10 Diagnosis: I95.0, I95.81, I95.89, I95.9, I95.2
Fatigue	Adverse events	Claims data	ICD-10 Diagnosis: R53.x, G93.3x

Nausea or vomiting	Adverse events	Claims data	ICD-10 Diagnosis: R11.x
Diarrhea	Adverse events	Claims data	ICD-10 Diagnosis: R19.7, K59.1

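### The inpatient definition and the once-per-day rule together can count one multi-day admission as several IP visits, up to one per day of stay

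*Protocol*

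**What the plan says.** Protocol Annex 2 defines the inpatient setting in one row, whose stated role is "Baseline characteristic, Outcome - HCRU". It therefore governs the outcome as well as baseline. The row has a facility part, "Any event in the inpatient table or an event in the non-inpatient table where acute_subacute is 'acute inpatient", and a professional part, which adds events "where utilization type is 'professional services', and service subcategory contains the term 'hospital/IP encounter".

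Section 9.7.3 measures HCRU as the "total number of per-patient-per-month (PPPM) IP, OP, ED, and pharmacy claims that occurred over the follow-up period". Its only de-duplication rule is "Medical claims will only be counted once per day to estimate visits". It then adds that "the total length of IP stays will be reported among patients with at least one IP visit".

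Table 3 in Section 9.3 lists the IP visit variable as a yes/no indicator and as "Number of IP (non-ED) visits (continuous"), all-cause and MM-related. It lists total duration of IP stays as a separate variable. Neither Table 3, Section 9.7.3 nor Annex 2 says how the claims or days of one admission become one visit.

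**The concern.** Counting medical claims once per day is a sensible proxy for outpatient and emergency contacts, which begin and end on one date. An admission spans several dates. Under the Annex 2 row, a professional hospital encounter on day 2 of a stay is an inpatient event in its own right. Under Section 9.7.3 it falls on a new day, so it counts again. The variable called number of IP visits then measures something between admissions and inpatient days with a claim, depending on how often such claims occur.

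All-cause and MM-related HCRU is primary Objective 3. Section 9.7 reports the counts by mean, SD, median and IQR, and Section 9.7.3 does so in three time windows. Because the inflation grows with length of stay, windows with different stay lengths are inflated by different amounts, and the inpatient share of all visits rises with it.

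**Working it through.** The protocol gives no expected visit count, so there is no figure to reproduce. The check applies the two written rules to one admission.

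**Inputs from the protocol**
- What qualifies as inpatient: the facility part and the professional part of the Annex 2 Inpatient row.
- How claims become visits: one count per day (Section 9.7.3).
- Merging of days within an admission: none stated.

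**Assumptions not in the protocol**
- The facility record is counted on one date.
- Each of the other L-1 days of the stay carries a qualifying professional claim with probability p. The protocol does not give p, so the full range is shown. The expected count needs only the average p over those days, not independence between days.

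**Formula**

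IP visits counted = number of distinct dates with a qualifying event, so the expected count is 1 + (L-1)p. Under an admission-level rule it is 1 for every L and p.

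| Stay (L days) | p = 0 | p = 0.25 | p = 0.5 | p = 0.8 | p = 1 |
|---|---|---|---|---|---|
| 3 | 1 | 1.5 | 2 | 2.6 | 3 |
| 5 | 1 | 2 | 3 | 4.2 | 5 |
| 8 | 1 | 2.75 | 4.5 | 6.6 | 8 |
| 14 | 1 | 4.25 | 7.5 | 11.4 | 14 |

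For example, L = 8 and p = 0.5 gives 1 + 7 × 0.5 = 4.5. Only p = 0 gives the right count for every stay. At p = 0.25 a 5-day stay already counts twice.

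**Does the count still separate visits from days?** Take two patients with eight inpatient days each, one with a single 8-day stay and one with four 2-day stays. At p = 1 the first scores 1 + 7 = 8 and the second 4 × (1 + 1) = 8, against 1 and 4 admissions. At p = 0.5 they score 4.5 and 4 × 1.5 = 6. As p rises, the visit count converges on the duration measure that Table 3 lists separately, and it loses the difference between one long stay and repeated admissions.

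**What the rules leave intact**
- The yes/no IP indicator: a patient with one admission is already a yes, so further days of that stay change nothing.
- Summed costs: each claim is paid once, and the visit rule does not multiply it.

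**The case against.** The strongest defence is that the Annex 2 row classifies setting and is not a counting rule. It uses the data vendor's own fields, and the protocol does not show whether an event is a claim line or an encounter already assembled. The professional part also has a plausible purpose. The Outpatient and Emergency rows both require an outpatient utilization type, so without it hospital professional services would belong to no medical setting for costs. Section 9.7.3 speaks only of estimating visits, the duration variable presupposes some notion of a stay, and Section 9.7 leaves detailed methods to the SAP.

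Part of this stands. The professional events should be kept for cost, and if they were already assembled into stays the inflation would shrink or vanish. But the written counting unit is the claim per day, and no text says that stays are assembled first. Section 9.8 commits the analysts to follow the protocol's codes and algorithms strictly, and Section 9.7 requires an amendment for a major change to a primary endpoint definition. This is a stated rule that gives the wrong unit, not detail left to the SAP.

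Several stronger readings are tempting, and the protocol does not support them:
- *Every admission counts as many visits as it has days.* That is the upper limit, reached only if a qualifying claim falls on every day, and the protocol gives no such frequency.
- *The step-up period is an 8-day admission counted eight times.* Table 4 defines that period as an assessment window, and Table 2 treats care setting as something to be described.
- *Observation stays are counted as IP visits.* That depends on what the vendor's subcategory contains, which the protocol does not say.
- *Total length of stay is left unadjusted for follow-up.* Section 9.7 foresees per-month reporting because follow-up varies, so asking for another summary is a preference.
- *The HCRU results cannot be interpreted at all.* The study is descriptive without formal comparisons, and the indicator, costs and duration are not distorted by this mechanism.

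**Conclusion.** The concern holds in a bounded form. As written, one multi-day admission can be counted as several IP visits, with one per day of stay as the ceiling. The expected overcount factor is 1+(L-1)p: between 1 and 5 for a 5-day stay and between 1 and 8 for an 8-day stay, with 3 and 4.5 at p = 0.5. These figures rest on an assumed claim frequency and on counting the facility record on one date. Where the truth lies in the range cannot be settled from the protocol.

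The affected results are the continuous all-cause and MM-related IP visit counts under primary Objective 3, and the total HCRU counts that include them.

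**What to change.** In Section 9.7.3 and the Annex 2 Inpatient row:
- Define an IP visit as one admission, merging overlapping, contiguous and transfer inpatient dates.
- Attach professional events dated within a stay to that stay for cost only, and do not count them as visits.
- Limit the once-per-day rule to OP and ED visits.

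The text change is one annex row and about one sentence, with modest reprogramming, and can be made before the final analysis planned for 27 February 2026. The downside is that IP counts will be lower than in earlier interim tables, so the final report should state the change of definition.
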